### **Optimal cut-off values**

To compare the performance of various quantitative PET evaluation parameters (such as lesion SUVmean, SUVmax and contrast), we will create receiver operating characteristic (ROC) curves and calculate sensitivity, specificity and accuracy values using validation results as a reference. Again, to test whether differences in sensitivity, specificity and accuracy between conventional and digital PET/CT are significant, we will apply the McNemar paired proportion test. A p value of less than 0.05 will be considered to indicate statistical significance. Finally, for each quantitative evaluation parameter, we will determine the optimal cut-off value to distinguish benign from malignant lesions on both conventional and digital PET/CT. This will be based on the value with optimal sensitivity and specificity (highest sum).

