## **1. INTRODUCTION AND RATIONALE**

In 2013, more than 100.000 people were diagnosed with cancer in the Netherlands [1]. For an effective treatment, accurate staging of cancer is of great importance. In recent years, Positron Emission Tomography imaging combined with Computed Tomography (PET/CT) (Figure 1A) using the radioactive tracer  $^{18}\text{F}$ -fluorodeoxyglucose (FDG) became important for staging, response monitoring and prognosis prediction in patients with cancer [2-4].

With FDG-PET/CT, the glucose consumption of the human body is visualised. Most tumors and inflammations have an increased glucose consumption (thus increased FDG uptake) as compared to healthy tissue. Therefore, FDG-PET/CT is able to characterize malignancies and lesions, find metastases and determine the reaction to treatment by visualizing the degree of glucose (FDG) uptake which then shows up on a PET scan as a 'hotspot'. However, the spatial resolution of current PET/CT systems is relatively low. This results in an underestimation of the true FDG uptake of small lesions, which limits the detection of small lesions and accurate staging [5]. Improvements in PET detector technology may lead to improved image quality, which may translate into a more accurate diagnosis and ultimately may improve patient management.

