### 2.2 Secondary objectives: image quality

*What is the image quality (in both quantitative and qualitative terms) of digital PET as compared to conventional PET?*

- 2.1 How do experienced readers rate digital PET image quality?
- 2.2 How does digital PET influence diagnostic confidence for N- and M-staging?
- 2.3 Are there differences in the appearance of normal tissues between digital and conventional PET?
- 2.4 What is the lesion detectability for digital PET as compared to conventional PET?
- 2.5 What is the optimal cut-off value of tumor uptake or lesion contrast to distinguish between benign and malignant lesions for digital PET, and how does this compare to conventional PET?
- 2.6 What are the optimal settings for digital PET to fulfill EANM procedure guidelines?
- 2.7 Do conventional and digital PET/CT studies, that both fulfill EANM procedure guidelines, provide comparable final PET/CT results?

Both the set of primary and secondary objective research questions can be studied in a variety of subgroups, based on tumor type, lesion size or other clinical factors.

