### **3. STUDY DESIGN**

We will perform a single center diagnostic accuracy study, in which patient-scans obtained using two types of PET/CT scanners (1 clinical study on the conventional system and 1 clinical study on the digital system) will be intra-individually compared.

Patient selection will be performed at the NM department in Isala. Patient eligibility will be based on the information provided by the referring specialist on the requisition for the clinical FDG-PET/CT study.

Patients will be included during the inclusion period of 6-12 months. Patients that meet the inclusion criteria and have signed informed consent will undergo two PET/CT scans on both the conventional and the digital PET system, immediately after each other. The scan order will be randomized per week:

- Week 1: first scan on conventional PET/CT, second scan on digital PET/CT.
- Week 2: first scan on digital PET/CT, second scan on conventional PET/CT. Etc.

For each patient, we start with a separate analysis of conventional and digital PET/CT images. One investigator will evaluate the PET/CT images quantitatively while two NM physicians will give qualitative (visual) judgments. Afterwards, we compare conventional and digital findings for all patients.

PET/CT data will be analyzed based on three subgroups of patients with lung cancer, breast cancer and esophageal cancer respectively. Pathology results and follow-up imaging by PET, CT, echography and MRI will be used as gold standard. When validation results are not available, conventional and digital PET/CT results are just compared with each other. More information on data analysis is described in section 5.2.

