### **5.2.3 Validation**

For each patient, the results of the PET/CT studies will be compared with available validation results. It is preferred that this regards invasive staging with pathology (PA) evaluation, although it may also include follow-up or information from other imaging modalities such as MRI and contrast-enhanced CT. Validation shall be performed based on findings from both conventional and digital PET/CT.

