**Inter-observer agreements**

Two NM physicians will evaluate conventional and digital PET/CT images on final diagnostic outcome, general image quality and diagnostic confidence. To evaluate the inter-observer variation between these two operators, we will compare percentage agreements and calculate a kappa.

Both the set of primary and secondary study parameters will be studied in a variety of subgroups, based on tumor type, lesion size and other clinical factors.

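### Section 7.1.2 names no cut-off for its McNemar test of quantitative lesion parameters; at the only cut-off rule given, each scanner's own highest-sum value, the test would not hold its 5% level

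*Combined protocol and SAP*

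**What the plan says.** Objective 2.5 (section 2.2) asks for the best cut-off of uptake or contrast "to distinguish between benign and malignant lesions for digital PET, and how does this compare to conventional PET".

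The analysis is in section 7.1.2 under Optimal cut-off values. ROC curves are drawn for lesion parameters such as SUVmean, SUVmax and contrast, and the three performance measures are calculated against the validation results. Then, "to test whether differences in sensitivity, specificity and accuracy between conventional and digital PET/CT are significant, we will apply the McNemar paired proportion test", with p<0.05 as the criterion. The cut-off appears only after that: "Finally, for each quantitative evaluation parameter, we will determine the optimal cut-off value", on both systems. The rule is: "This will be based on the value with optimal sensitivity and specificity (highest sum".

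The number of lesions with a reference result is not given. Section 5.2.3 says "For each patient, the results of the PET/CT studies will be compared with available validation results", and section 3 adds: "When validation results are not available, conventional and digital PET/CT results are just compared with each other". The closing statement of section 7.1.2 says that all study parameters "will be studied in a variety of subgroups, based on tumor type, lesion size and other clinical factors".

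**The concern.** A continuous measure has no sensitivity or specificity until a cut-off is fixed, and the plan fixes none for its test. The one rule it contains picks a cut-off for each scanner from the lesions that are then tested. McNemar assumes that the positive/negative rule was set beforehand. A highest-sum cut-off is unstable, so chance alone can put two identical scanners at different points of the same ROC curve. Their classifications then differ systematically, and the test reads that as a scanner difference.

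At stake is the performance comparison for quantitative parameters. In addition, objective 2.5 asks how the two cut-offs compare, and the plan gives no interval for that difference.

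**Working it through.** **1. What the plan supplies.** It gives the McNemar test, p<0.05 (sidedness not stated, taken as two-sided) and the highest-sum rule for each scanner. It states no sample size or error rate for this analysis. The sign-test sizes in section 4.4 (49, 79, 28 and 42) reproduce exactly, but they serve other objectives.

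**2. What must be assumed.** Lesion counts, malignant share, separation and between-scanner correlation are not in the documents. Assumed: identical scanners, normal markers with equal SD in malignant and benign lesions, independent lesions, correlation 0.8-0.9. Separation d corresponds to an ROC area of Φ(d/√2): 0.86 at 1.5 SD, 0.92 at 2 SD and 0.96 at 2.5 SD.

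**3. Formulas.** The cut-off c maximises Se(c) + Sp(c). Exact McNemar: p = 2·P(Bin(b+c′, ½) ≤ min(b, c′)), where b and c′ are the discordant counts.

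**4. Mechanism by hand.** With 60/30 to 200/100 malignant/benign lesions and separation 1.5-2 SD, the cut-offs of identical scanners differ by 0.20-0.30 SD on average by chance. Take separation 1.5 SD and cut-offs of 0.60 and 0.90, either side of the true optimum of 0.75.

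- Scanner A: Se = Φ(1.5 − 0.60) = Φ(0.90) = 0.816; Sp = Φ(0.60) = 0.726.
- Scanner B: Se = Φ(1.5 − 0.90) = Φ(0.60) = 0.726; Sp = Φ(0.90) = 0.816.

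The sums are equal. Sensitivity and specificity each differ by 0.090, in opposite directions. At correlation 0.9 the bivariate normal gives discordant shares among malignant lesions of 0.1105 and 0.0203.

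- 200 malignant lesions: about 22 against 4, p = 2·P(Bin(26, ½) ≤ 4) = 0.0005.
- 60 malignant lesions: about 7 against 1, p = 2·(1 + 8)/256 = 0.07.

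The same chance gap in cut-offs is therefore significant in the larger sample and not in the smaller one.

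**5. Simulated false-positive rate for sensitivity, own cut-offs, exact test.**

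| Malignant/benign | Separation 1.5-2 SD | Separation 2.5 SD |
|---|---|---|
| 15/10 | 0.3%-1.9% | not tabulated |
| 25/10 | 4.3%-12.2% | 1.4%-1.5% |
| 40/20 | 9.2%-23.3% | 3.9%-4.6% |
| 60/30 | about 20%-34% | about 10%-12% |
| 100/50 | about 28%-43% | 19.4%-21.2% |
| 200/100 | about 40%-53% | 29.7%-33.1% |

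Runs used 1,000 to 2,000 trials per setting; the Monte Carlo standard error is at most 1.1 points at 2,000.

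**6. Case mix.** The table has 60% to 67% malmalignant share in its first row and 67% to 71% in the others. Outside that range:

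- 45/45, separation 2-2.5 SD: sensitivity about 2%-12%.
- 30/60, separation 1.5-2 SD: sensitivity about 3%-9%, specificity about 20%-31%.
- 80/10, separation 1.5-2 SD: accuracy about 28%-40%. At 60/30 to 200/100 it was 1.2%-14.3%.

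**7. Cause.** With one cut-off fixed beforehand for both scanners, the same exact test gave 0%-4.3% in every setting. The excess comes from estimating the cut-offs, not from McNemar itself.

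**The case against.** **The plan does not say that McNemar is run at the own cut-offs.** The test comes first and the cut-off step last, so a reader might infer a prescribed error where the documents show only an unspecified threshold. This stands as a limit on the claim. It does not rescue the plan: no other threshold is given, and leaving it open lets the cut-off be chosen after the data are seen.

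**The percentages rest on assumed inputs.** This also stands. A reader might take 20%-53% as the error rate for any 90 to 300 lesions. It is not: it needs separation near 1.5-2 SD and roughly half to two-thirds or more malignant lesions. With 90 lesions and 30% malignant, sensitivity was at 0.5%-10%.

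**The artefact is usually harmless to the overall conclusion.** A reader might infer that the plan would falsely declare digital PET superior. In most settings it would not: sensitivity and specificity move in opposite directions, and both were significant in the same direction in at most 0.05% of trials at about two-thirds malignant. The reassurance is not general, because accuracy is affected when benign lesions are very few.

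**One common cut-off would be simpler.** For identical scanners a pooled common cut-off gave 0%-3.6%. A reader might think it must be ruled out because a shift in uptake scale alone makes it significant: with identical ROC curves (separation 1.5 SD, correlation 0.9) and a 0.2 SD shift, sensitivity or specificity differed significantly in 14% (60/30) to 74% (200/100) of trials. But at one fixed cut-off such a shift is a real change in sensitivity or specificity, not a false positive. The protocol gives reason to expect a shift: of low resolution it says "This results in an underestimation of the true FDG uptake of small lesions". So a common cut-off is legitimate but answers a different question.

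**It is one secondary objective in an initial assessment.** True, and it limits the consequence.

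**Conclusion.** The point holds in this form. The plan leaves the cut-off for its McNemar test open, and following the only rule it contains would break the 5% level once lesion numbers are moderate. The size depends on lesion count, malignant share, separation and correlation, none of which the documents give, so the figures are illustrations and not bounds. More lesions make the problem worse: even at 2.5 SD, 200/100 gives about 30%-33%. At 15/10, or at 25/10 and 40/20 with separation 2.5 SD, the test stays below 5%. Clustering of lesions within patients was not modelled in these rates.

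The effect is confined to the quantitative analysis behind objective 2.5. The reader-based McNemar test in section 7.1.1 uses no estimated cut-off and is untouched, as are the sample sizes in section 4.4. The change should be made before analysis.

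**What to change.** In section 7.1.2, Optimal cut-off values:

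1. For each parameter, compare the scanners on paired ROC areas with a bootstrap that resamples patients, in place of McNemar at separately estimated cut-offs.
2. For objective 2.5, report each scanner's highest-sum cut-off and the difference between them, with intervals from a patient-level bootstrap that re-selects both cut-offs in every resample. Show the three performance measures at those cut-offs together and descriptively, noting that in-sample values are optimistic.
3. If a point comparison at one common, pre-specified cut-off is wanted, state that it asks whether the same uptake threshold performs alike on both scanners, and that a difference in uptake scale alone can make it significant.

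Cost: SAP wording and a script; no new data. The ROC-area comparison concerns whole curves, not one operating point. In simulation its bootstrap was slightly liberal (4.7%-6.3%), with power of 81% (100/50) and 99% (200/100) when one scanner truly separates 0.3 SD better. Intervals will be wide: for the cut-off difference about 1.4 SD at 60/30 and 0.9-1.1 SD at 200/100, with conservative coverage (99.2%-100%).

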### **EANM procedure guidelines**

It is expected that both conventional and digital PET/CT studies, which fulfill EANM procedure guidelines, provide a comparable PET/CT diagnostic outcome. These results will be evaluated for all patients. Differences in diagnostic outcome will be assessed using the sign-test and the Wilcoxon signed-rank test.

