##### Sample size calculation for patients with lung cancer and patients with breast cancer:

###### **Objective 1.1 What is the difference in the number of lymph node metastases?**

*For power-calculations we translated this question into: does digital PET detect more, fewer or identical numbers of lymph node metastasis? We would like to be able to detect a 20% difference, if present. This level is generally considered relevant in obtaining a new type of scanner. Using the two-tailed sign-test, assuming a power of 80% and a p value of 0.05, this requires the inclusion of 49 subjects. After applying the 10%-correction for the inclusion of negative PET/CT scans, the number of required subjects is 54.*

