**Objective 1.3 What is the difference in the N status?**

*For power-calculations we translated this question into: is the N-status on digital PET equal, lower or higher as compared to conventional PET? We would like to be able to detect a 16% difference, if present. Using the two-tailed sign-test, assuming a power of 65% and a p value of 0.10, this requires the inclusion of 42 subjects. After applying the correction for negative PET/CT scans, the number of required subjects is 46.*

From all above calculations, we aim to include 90 patients with lung cancer, 90 patients with breast cancer and 45 esophageal cancer patients, for a total of 225 patients.

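### Objective 2.7 asks whether EANM-compliant scans are comparable, but the EANM analysis names only tests for a net shift and gives no agreement estimate or criterion

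*Combined protocol and SAP*

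**What the plan says.** All references are to the combined protocol and SAP.

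- **The question.** Objective 2.7 (section 2.2) reads: "Do conventional and digital PET/CT studies, that both fulfill EANM procedure guidelines, provide comparable final PET/CT results".
- **The expectation.** Section 7.1.2, EANM procedure guidelines: "It is expected that both conventional and digital PET/CT studies, which fulfill EANM procedure guidelines, provide a comparable PET/CT diagnostic outcome".
- **The analysis set.** The same paragraph adds: "These results will be evaluated for all patients". Section 4.4 sets the target: "we aim to include 90 patients with lung cancer, 90 patients with breast cancer and 45 esophageal cancer patients, for a total of 225 patients".
- **The analysis.** The paragraph ends: "Differences in diagnostic outcome will be assessed using the sign-test and the Wilcoxon signed-rank test". It gives no agreement statistic, confidence interval, margin or decision rule.
- **Related text.** Section 5.2.4 has two physicians give a final diagnostic outcome for each EANM dataset, to be compared, without a criterion. Section 7.1.1 plans percentage agreement between the two systems, but under the primary objective. Kappa appears in section 7.1.2 (General PET image quality and Inter-observer agreements) only as a measure between the two readers. Section 4.4 calculates sample sizes for objectives 1.1 and 1.3 only.

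**The concern.** The question is one of similarity, and the tests named for it are tests of difference. Two problems follow.

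First, failing to reject no shift does not show that the shift is small. The smaller the group, the more likely that failure is, whatever the truth.

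Second, the sign test drops patients whose outcome is the same on both scanners and compares the number higher with the number lower. The Wilcoxon test does the same with weights for the size of the change. Neither measures how many patients change. A scanner pair that restages many patients in both directions can give p near 1. Section 7.1 says that every disagreement in T, N or M stage counts as a difference, yet under these tests opposite disagreements cancel.

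The outcome comparison carries much of the EANM validation, because section 5.2.4 urges caution over the quantitative EANM comparison on account of the delay between scans. Section 9.6 says that study results may support marketing and regulatory claims.

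**Working it through.** **Inputs.** Group sizes 225, 90, 90 and 45 (section 4.4). The EANM paragraph states no significance level, so two-sided 0.05 is assumed, as in the lung and breast calculations. The documents give no rates of change between scanners, so the rates below are assumptions.

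**Step 1: reproduce the plan's own sign-test figures.** For objective 1.1 the plan says "We would like to be able to detect a 20% difference, if present" and "Using the two-tailed sign-test, assuming a power of 80% and a p value of 0.05, this requires the inclusion of 49 subjects". Read the difference as a probability of 0.5 + 0.20 = 0.70 that a changed patient is higher on digital. The exact two-sided sign test then has power 81.0% at n = 49. For objective 1.3 (0.5 + 0.16 = 0.66), power is 80.7% at n = 79. The esophageal figures at 0.10 also reproduce: 68.3% at n = 28 and 66.0% at n = 42. The method therefore matches the plan's. These calculations treat every subject as an untied pair; patients with identical outcome on both scanners reduce the effective number.

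**Step 2: fixed examples in the full set.** Suppose 75 of 225 patients change outcome: 75/225 = 33.3%, exact 95% CI 27.2-39.9%. With m changed patients and k in the larger direction (k > m/2), the sign-test p-value is 2 × P(X ≥ k), X ~ Binomial(m, 0.5), capped at 1. The Wilcoxon values assume one-step changes and the normal approximation.

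| Higher / lower | Sign test p | Wilcoxon p |
|---|---|---|
| 38 / 37 | 1.00 | 0.91 |
| 45 / 30 | 0.105 | 0.083 |
| 46 / 29 | 0.064 | 0.0496 |

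So a third of patients can change with both tests non-significant, up to a split of about 45 to 30. Beyond that the tests begin to react. At the other extreme, if all changes go one way, 6 changed patients suffice: 2 × 0.5^6 = 0.031.

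**Step 3: probability of a non-significant sign test.** Let u and d be the proportions higher and lower. The number changed is m ~ Binomial(n, u + d); given m, the number higher is Binomial(m, u/(u + d)). Averaging the exact test over m gives:

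| Assumed change | n = 45 | n = 90 | n = 225 |
|---|---|---|---|
| 15% higher, 15% lower | 97.4% | 97.0% | 96.2% |
| 25% higher, 25% lower | 97.1% | 96.4% | 96.0% |
| 15% higher, 5% lower | 79% | 51% | 8.5% |

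In the first two rows there is no net shift, so the test is doing its job. It does not respond to the 30% or 50% of patients whose outcome differs, and a larger sample does not help. In the third row there is a net shift of 15 − 5 = 10 percentage points. The full set usually finds it; the tumor-type groups often do not.

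**Step 4: what an estimate would show.** In the 75-of-225 example, agreement is 150/225 = 66.7%, exact 95% CI 60.1-72.8%, whichever way the changes go. With 81 of 90 patients identical, agreement is 90%, exact 95% CI 82-95%.

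**The case against.** **The plan does not equate non-significance with comparability.** This stands. A reader might infer that p ≥ 0.05 will be reported as comparable, because comparability is the expected result and these are the only tests named. The documents state an expectation and say that differences will be assessed; they do not draw that conclusion. What can be shown is a missing criterion, not a wrong planned conclusion.

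**The blind spot needs nearly balanced change.** This stands too. Nothing in the documents says that 15% or 25% would move each way. With 75 changed patients and a true 70:30 split, the sign test is non-significant only 7% of the time. The stated analysis set is all patients, where the 15%/5% shift is found in 100 − 8.5 = 91.5% of trials. The weaker figures belong to the analyses by tumor type, which the closing paragraph of section 7 also plans.

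**Agreement is already in the plan.** This stands in part. Section 7.1 counts disagreements in either direction, section 5.3.2 lists patient-based and lesion-based reader comparisons of the EANM scans, and section 7.1.1 plans percentage agreement between systems. A reader might infer that objective 2.7 cannot be answered at all. That goes too far: the paired outcomes are collected and the statistic could be extended to them. But the EANM paragraph repeats the two tests without the percentages, and no confidence interval or criterion is attached anywhere.

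**This is one of seven secondary objectives in an initial assessment.** True, and it limits the weight of the point, though the correction takes only a few sentences.

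**Conclusion.** The concern holds in a limited form and should be corrected. The analysis named for objective 2.7 tests for a net directional shift, while the question is whether outcomes are comparable. It neither estimates how often outcomes differ nor says what would count as comparable.

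The size depends on the pattern of change. Under assumed balanced change the sign test is non-significant in 96-97% of trials at every planned group size. Under an assumed 15%/5% shift the miss rate is small in the full set and large in the tumor-type groups. These figures rest on a two-sided 0.05 level and assumed rates of change.

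Two stronger readings are not supported: that a finding of comparability is almost assured, and that the tests would miss any change affecting a third of patients. Both fail once change is mainly in one direction in the full set.

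**What to change.** In section 7.1.2, EANM procedure guidelines:

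1. Make the main analysis for objective 2.7 the percentage of patients with identical N, M and TNM outcome on the two scanners, the between-scanner weighted kappa, and the net difference (percentage higher minus percentage lower on digital), each with a 95% CI. The net difference alone is not enough, since balanced changes cancel there as well.
2. Keep the sign and Wilcoxon tests as supportive, and state that a non-significant result will not be taken as comparability.
3. Report the two readers' agreement on the same scan alongside, as context. If this or any other limit is to serve as an acceptance criterion, it is a margin: justify it and fix it before the data are read. Inter-reader agreement would be a lenient margin if the readers agree poorly.
4. Confirm that each reader's EANM outcome is recorded separately, since item 3 depends on it.

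The cost is SAP wording and a little extra analysis; no additional scans are needed. The downside is that in groups of 45 to 90 the interval may be too wide to claim comparability, as the 82-95% for 81 of 90 shows.
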